## 1.9.4.2 Multiple imputations

Loss of PASI 75 response will be evaluated as described above in section 1.9.2 with multiple imputations instead of non-responder imputation for missing values. Multiple imputation will also be used for PASI/IGA score and responses variables.

Novartis	Confidential	Page 41
RAP Module 3	9-Apr-2018 (1:15)	Secukinumab / AIN457A2302E1

Multiple imputation (MI) is a simulation based approach where missing values are replaced by multiple Bayesian draws from the conditional distribution of missing data given the observed data and covariates, creating multiple completed data sets. These completed data sets can then be analyzed using standard methods. Rubin (1987) presented rules how to combine the multiple sets of estimates to produce overall estimates and confidence intervals that adequately incorporate missing data uncertainty.

Missing values for the 'change from baseline PASI score' will be imputed based on an underlying normal distribution and using a Markov Chain Monte Carlo (MCMC) method. The change from baseline in PASI score appears to follow closer to a normal distribution than the actual PASI score.

The imputations will be done separately for each treatment group including baseline weight, failure to at least one previous biologic (yes/no), and number of previous systemic therapies as additional covariates. Values post assessment timepoint of the primary endpoint will not be considered for imputations.

The number of imputations will be set to 100, the seed for the random function will be set to 457230201 for this study. To generate the multiple imputed data sets, the SAS procedure MI can be used as follows:

The input data set <pasi> should have one record per subject with baseline PASI as well as all changes from baseline PASI score.

ODS LISTING CLOSE;

PROC MI DATA=<pasi> OUT=<impdata> SEED=457230201 NIMPUTE=100; EM maxiter=300; VAR <baseline weight> <failure to at least one biologic> <number of previous systemic therapies> <baseline PASI> <change from baseline PASI week 52> <change from baseline PASI week 56> <change from baseline PASI week 60> <change from baseline PASI week 64> <change from baseline PASI week 64> <change from baseline PASI week 68> BY <treatment group>; RUN;

ODS LISTING;

Novartis	Confidential	Page 42
RAP Module 3	9-Apr-2018 (1:15)	Secukinumab / AIN457A2302E1

The imputed data are saved in data set <impdata>. The outcomes of interest, i.e. the loss of PASI 75 response will be calculated from change from baseline PASI scores. The day of visit at which the first occurrence of losing PASI 75 response will also be obtained. In the case of missing visits or visit dates the planned visit day will be used., e.g. as follows:

DATA <impdata2>; SET <impdata>; IF <change from baseline PASI week primary endpoint>/<baseline PASI>=0.75 THEN <PASI 75 response>=1; ELSE <PASI 75 response>=0; END; RUN;

The treatment differences for each imputed data set will then be evaluated by using Cox proportional hazards regression as described section 1.9.2. This analysis will be done by \_IMPUTATION\_ for each pairwise comparison as described in section 1.9.5. The data set should be sorted such that the control group comes last. E.g as follows:

```
ods table HazardRatios = hazardratios
proc phreg data = <impdata2>;
class <treatment group> <core study> <geographical region> <body weight stratum>
model TIME*PASI75(1)= <treatment group> <core study> <core baseline PASI> <extension baseline PASI>/ties=exact;
STRATA < geographical region> < body weight stratum>
by _Imputation ;
run:
      data dhazardratios:
            set hazardratios;
            where Description in ( 'TRT01PN 1 vs 3' 'TRT01PN 2 vs 4');
            if Description in ( 'TRT01PN 1 vs 3') then comp =1;
            else if Description in ('TRT01PN 2 vs 4') then comp =2;
            if HazardRatio NE . and HazardRatio > 0 then ESTIMATE=log(HazardRatio);
            if WaldLower NE . and HazardRatio > 0 then STDERR=log(WaldLower/HazardRatio)/-probit(1-0.05/2);
            if missing(ESTIMATE) or missing(STDERR) then delete;
     effect="LogHR";
      run;
```

• The PHREG procedure and following MIANALYZE procedure could then be run with by-variables for the comparison and response identifier.

The MIANALYZE procedure expects the parameter estimate in the variables ESTIMATE, and the corresponding standard error in the variable STDERR. The dataset dhazardratios above contained the estimate and its standard error for log(Hazard ratio)

The estimates and standard errors of the log of hazard ratio based on the 100 imputed data are then combined by applying Rubin's rules for multiple imputed data sets, see Little and Rubin (2002).

The SAS procedure MIANALYZE will be applied as follows:

ODS LISTING CLOSE; ODS OUTPUT ParameterEstimates=<results>; PROC MIANALYZE PARMS=<lgparms>; BY comp; MODELEFFECTS LogHR; RUN; ODS LISTING;

DATA <results2>; SET <results>; or=EXP(estimate); lowercl=EXP(LCLmean); uppercl=EXP(UCLmean); KEEP <By-variables> or lowercl uppercl probt; RUN;

- 1. **Cumulative Probabilities and CI:** Use log(-log(x))-transformed estimates for the survival function and their associated standard errors for each imputed data set and combine the results using Rubin's rules (PROC MIANALYZE). The transformation is done to ensure that resulting confidence intervals only include values between 0 and 1.
  - 1. Then back-transform combined estimates and associated CI intervals and calculate the 'cumulative' quantities.
  - 2. Calculate the mean across all imputed data sets for the columns: "subj. at risk" / "subj. with event" / "subj. with event/at risk"/ "cum. subj. with event", round them to the nearest integers as these will generally be non-integers.

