#### 1.9.1.1 Definition of PASI and related variables

The total BSA affected by plaque-type psoriasis was estimated from the percentages of areas affected, including head, trunk, upper limbs and lower limbs (see below for PASI assessment). The following calculations were done: each reported percentage was multiplied by its respective body region corresponding factor (head = 0.1, trunk = 0.3, upper limbs = 0.2, lower limbs = 0.4). The resulting 4 percentages will be added up to estimate the total BSA affected by plaque-type psoriasis. The PASI scoring system is further described in Table 1-12.

A PASI score (Fredriksson and Pettersson 1978, Weisman et al 2003, Gottlieb et al 2005) was derived as indicated in Table 1-12. The head, trunk, upper limbs and lower limbs are assessed separately for erythema, thickening (plaque elevation, induration), and scaling (desquamation). The average degree of severity of each sign in each of the four body regions is assigned a score of 0-4. The area covered by lesions on each body region is estimated as a percentage of the total area of that particular body region. Further practical details help the assessment:

Novartis	Confidential	Page 30
RAP Module 3	9-Apr-2018 (1:15)	Secukinumab / AIN457A2302E1

- 1. The neck is assessed as part of the head.
- 2. The axillae and groin are assessed as part of the trunk.
- 3. The buttocks are assessed as part of the lower limbs.
- 4. When scoring the severity of erythema, scales should not be removed.

Because the head and neck, upper limbs, trunk and lower limbs correspond to approximately 10%, 20%, 30% and 40% of the body surface area, respectively, the PASI score was calculated using the formula:

 $PASI = 0.1 (E_h + I_h + D_h)A_h + 0.2 (E_u + I_u + D_u)A_u + 0.3 (E_t + I_t + D_t)A_t + 0.4 (E_l + I_l + D_l)A_l$ 

where E, I, D, and A denote erythema, induration, desquamation, and area, respectively, and h, u, t, and l denote head, upper extremities, trunk, and lower extremities, respectively (see Table 1-10).

PASI scores can range from a lower value of 0, corresponding to no signs of psoriasis, up to a theoretic maximum of 72.0.

The investigator was only responsible for collecting the components or scoring signs and total regional area. PASI calculations were done via the PASI Score eCRF.

The PASI scores calculated via the PASI Score eCRF will be used in the analysis and for derivation of PASI response values, relapse and rebound (see below).

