#### Table 1-2 The PASI scoring system

\* Percentage (not score) of body region (not whole body) affected will be entered in the eCRF

+ Neck is assessed as part of the Head (H) body region.

‡ Axillae and groin are assessed as part of the Trunk (T) body region.

§ Buttocks are assessed as part of the Lower limbs (L) body region.

The following definitions are possible efficacy evaluations that can be used in clinical trials in psoriasis (CHMP/EWP/2454/02, 2004):

- **PASI non response:** subjects achieving <50% improvement (reduction) in PASI score compared to baseline are defined as PASI non responders
- **Partial response**: subjects achieving ≥ 50% improvement (reduction) in PASI score but less than 75% compared to baseline are defined as partial responders
- **PASI 50 response**: subjects achieving ≥ 50% improvement (reduction) in PASI score compared to baseline are defined as PASI 50 responders
- **PASI 75 response**: subjects achieving ≥ 75% improvement (reduction) in PASI score compared to baseline are defined as PASI 75 responders

Novartis	Confidential	Page 32
RAP Module 3	9-Apr-2018 (1:15)	Secukinumab / AIN457A2302E1

- **PASI 90 response**: subjects achieving ≥ 90% improvement (reduction) in PASI score compared to baseline are defined as PASI 90 responders
- **PASI 100 response**: complete clearing of psoriasis (PASI=0)
- **Relapse**: when the achieved maximal PASI improvement from baseline PASI in core is reduced by >50%
- **Rebound-like event**: defined as increase of PASI of more than 25% from baseline value or occurrence of new pustular, new erythrodermic or more inflammatory psoriasis **after** stopping therapy
- Rebound: defined as rebound like event occurring within 8 weeks of stopping therapy

The analysis of rebound will be done for the follow-up period.

The number and percentage of subjects experiencing rebound and rebound like events will be presented by treatment group as follows:

- For rebound, all assessments done up to 8 weeks will be summarized.
- Similarly for rebound like events, all assessments done up to 12weeks will be summarized.
  - 1. Rebound up to 8 weeks: For this time-point the worst outcome (i.e. rebound like event=yes) prior to this cut-off is considered (e.g. if a subject had >25% PASI increase at Week 260, but not at Week 264 the subject would be considered as rebounder for this "up to 8 week timepoint").

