## For the final analysis

For subjects who prematurely discontinue treatment, but are observed in the follow-up period, efficacy data collected in follow-up periods will not be linked to planned study visits.

The following missing data imputation methods will apply to PASI and IGA score or response variables in the final analysis:

- Response variables based on PASI score and IGA mod 2011 categories will be generally be presented as 'observed case'; i.e. all available data for each time point will be included in the analyses.
- For subjects who received secukinumab dose from week 52, multiple imputation will be used as the sensitivity method

Novartis	Confidential	Page 40
RAP Module 3	9-Apr-2018 (1:15)	Secukinumab / AIN457A2302E1

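### Multiple imputation of PASI change from an unbounded normal model never gives PASI = 0, so for PASI 100 it reproduces non-response; the SAP also gives no model for imputing IGA

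*SAP*

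**What the plan says.** **The model.** SAP 1.9.4.2: "Missing values for the 'change from baseline PASI score' will be imputed based on an underlying normal distribution". Draws are by MCMC, separately by treatment group. The stated reason is that change looks closer to normal than the score does.

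**The code.** It is introduced by "To generate the multiple imputed data sets, the SAS procedure MI can be used as follows". The call begins "PROC MI DATA=<pasi> OUT=<impdata> SEED=457230201 NIMPUTE=100; EM maxiter=300; VAR <baseline weight>" and ends "<change from baseline PASI week 68> BY <treatment group>; RUN". Between these are two treatment-history covariates, baseline PASI and the PASI changes from Week 52. There is no minimum, maximum or rounding option, and no IGA variable. The only response derived afterwards is PASI 75 and its loss.

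**The scope.** The same section adds: "Multiple imputation will also be used for PASI/IGA score and responses variables".

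**The scale.** SAP 1.9.1.1: "PASI scores can range from a lower value of 0, corresponding to no signs of psoriasis, up to a theoretic maximum of 72.0". PASI 100 response is "complete clearing of psoriasis (PASI=0"). An IGA 0/1 response needs an IGA score of 0 or 1 and a gain of at least 2 points.

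**Where MI is used.** In SAP 1.9.4, final analysis, observed case is the main presentation. For subjects on secukinumab from Week 52, "multiple imputation will be used as the sensitivity method". For the RW re-run, SAP 1.9.4 assigns MI to PASI- and IGA-based responses, but its later paragraph on last observation carried forward says these responses get non-response. SAP 1.9.4.1 sets out non-responder steps for Weeks 52 to 156, and Protocol 9.4.3 also specifies non-response.

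**The concern.** Among responders, PASI piles up at exactly 0 and cannot go below it. A normal model for change has no such pile and no floor. It can place values near or below 0 but never on it, and PASI 100 is defined by that one point.

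In the final response tables, MI is the only sensitivity method named against observed case. For PASI 100 it would not test robustness to missing data, because it would classify every missing value as a failure. All 100 completed data sets would then give the same PASI 100 count. The between-imputation variance would be zero, and the interval would carry no missing-data uncertainty. A reader seeing a table labelled multiple imputation would assume otherwise.

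The SAP also leaves room for different programmers to report quite different PASI 100 rates, depending on an unstated rule for negative or near-zero draws. The promised imputation of IGA has no model at all.

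**Working it through.** The documents give no figure to reproduce. The check is one step of logic, one identity, and simulation under stated assumptions.

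**1. Logic.** Imputed PASI = baseline + normal draw. This is continuous, so P(imputed PASI = 0) = 0. Under the SAP definition no imputed value is PASI 100.

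**2. Size under the literal definition.** Let m be the missing fraction and p the true PASI 100 rate among the missing. Shortfall in the arm's rate = m × p. Both inputs are assumptions:
- m = 0.15, p = 0.10: 0.15 × 0.10 = 1.5 points
- m = 0.15, p = 0.40: 0.15 × 0.40 = 6.0 points

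**3. Simulation of the SAP model.** Bayesian normal-regression MI with the SAP's 100 imputations. Predictors were baseline PASI and the earlier changes; the three other covariates were left out. Arms had 276 subjects (the planned active arm), with 15% missing at random at Week 68 and 20 replicates per setting. Assumed: baseline PASI mean 22, SD 9, floor 12; mean residual PASI 8% or 15% of baseline in subjects not clear.

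| True PASI 100 among the missing | Residual setting | Imputed exactly 0 | Rounded to 0.1, equal to 0 | Imputed below 0 |
|---|---|---|---|---|
| 22.7% | 8% | 0.0% | 2.2% | 19.8% |
| 20.5% | 15% | 0.0% | 1.3% | 19.1% |
| 32.0% | 8% | 0.0% | 2.2% | 23.7% |
| 33.8% | 15% | 0.0% | 1.3% | 22.4% |
| 42.2% | 8% | 0.0% | 2.6% | 25.7% |
| 39.8% | 15% | 0.0% | 1.5% | 25.4% |
| 49.7% | 8% | 0.0% | 2.8% | 28.6% |
| 50.4% | 15% | 0.0% | 1.7% | 28.8% |

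**4. Reading PASI 100 as at least 100% improvement.** The last column is then the imputed PASI 100 rate, and every counted value is a score the scale does not allow. The gap among imputed values runs from 20.5 − 19.1 = 1.4 points to 50.4 − 28.8 = 21.6 points. At 15% missing that is 0.15 × 1.4 = 0.2 to 0.15 × 21.6 = 3.2 points on the arm's rate. A second simulation at high clearance gave about 18–21% against a true 28–34%.

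**5. Placebo-like arms under the same reading.** One simulation gave about 8–9% against a true 8–10%. Another, with 138 subjects, skewed PASI and a true rate of about 3–16%, gave 6–21%, above the true rate in 19 of 24 settings. The direction is not general.

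**6. PASI 90 and PASI 75.** Among imputed values, PASI 90 was 1–6 points too low in high-clearance settings and about 3–13 points too high in the 24 placebo-like ones. At 15% missing that is 0.15–0.9 points low or 0.45–1.95 points high on the arm's rate. In the high-clearance settings PASI 75 was within 1 point, because its threshold lies away from 0.

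**7. IGA.** IGA 0/1 cannot be derived from a data set that holds no IGA score.

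**The case against.** **The code is an example for another endpoint.** It is offered as something that can be used, it serves loss of PASI 75, and its list stops at Week 68. That stands, and it means the final tables need further specification anyway. But the normal model is stated in prose as what will be done, MI is extended to the response variables, and neither text nor code supplies a bound or a PASI 100 rule.

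**A programmer may use a cut-off of at least 100% improvement.** The PASI 75 code works from change divided by baseline, so this is plausible. A reader might infer that no missing value can become PASI 100 under any programming; the documents do not support that, because the result depends on the literal definition. A reader might equally infer that the alternative reading is always too low; steps 4 and 5 show that this depends on the clearance rate.

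**MI may not govern the RW re-run.** A reader might take MI as the settled method there. The SAP contradicts itself, and Protocol 9.4.3 sides with non-response. Under non-response a missing value is also never PASI 100, but by declared design.

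**The consequence is limited.** This stands. In the final analysis MI is a sensitivity method and the response summaries are descriptive. Secondary endpoints lie outside the testing strategy (Protocol 9.4.2, SAP 1.9.3).

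**IGA is a separate matter.** Also fair. Its absence from the variable list is a specification gap, not an effect of the normal model.

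**Conclusion.** The point holds in this form. Under the SAP's definition of PASI 100, its MI model never imputes a PASI 100 response, so the MI sensitivity analysis of the final PASI 100 tables is non-responder imputation in effect. That follows from the definition alone and needs no assumed parameter.

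The size does rest on assumptions: 1.5 to 6 points at 15% missing and a true rate of 10–40% among the missing. Under the at-least-100% reading the bias is downward where clearance is high and small or of either sign in placebo-like arms. Final-analysis MI covers only subjects on secukinumab from Week 52, so the placebo-like case matters mainly if MI is kept for the RW re-run.

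A reader might infer that the primary endpoint is at risk. It is not: PASI 75 and loss of PASI 75 are barely touched. This should be corrected, but it does not threaten the trial's main conclusion.

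**What to change.** 1. For PASI 90 and PASI 100, impute the PASI score itself by predictive mean matching within treatment group (fully conditional specification, FCS), and derive the responses from the imputed score. Borrowed scores keep the zeros and cannot be negative. Do not match on change: a cleared donor with baseline b_d has change −b_d, and giving that to a recipient with baseline b_r yields b_r − b_d. This is zero only if the baselines agree, and negative if b_r is smaller.
2. Do not rely on setting negative draws to 0. That gives the same PASI 100 rate as the at-least-100% reading.
3. Give IGA its own ordinal or logistic FCS model, for example with earlier IGA and PASI as predictors.
4. State whether MI or non-response governs PASI and IGA responses in the RW re-run, and align SAP 1.9.4 and 1.9.4.1 with Protocol 9.4.3 or record the change.

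The cost is minor SAP rewording and reprogramming of the imputation step. No new data are needed.

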### 9.4.3 Handling of missing values/censoring/discontinuations

For the primary analysis subjects who did not lose PASI 75 response before Week 68 but with missing values at Week 68 will be considered as censored. Other time-to-event analyses will be handled analogously.

For other analyses (not time to event) missing values with respect to response variables based on PASI score and IGA mod 2011 score will be imputed with non-response regardless of the reason for missing data (e.g., premature study discontinuation, missed visit, administrative issues).

Following the intent-to-treat principle for subjects who prematurely discontinue treatment, but who are observed in the follow-up period, efficacy data collected in follow-up periods will be linked to planned but missed study visits as well, following imputation schemes described in the analysis plan (e.g., if a subject discontinues treatment at Week 56, but has follow-up visit F4, the PASI score observed at Visit F4 might be used for Week 60 assessments).

The last observation carried forward method will be applied to PASI score and IGA mod 2011 score. Note, that responses based on PASI score or IGA mode will be imputed differently as described above.

If all post Randomization Visit efficacy values are missing for one efficacy parameter then these missing values will not be imputed and this subject will be removed from the analysis of the corresponding variable, *i.e.*, it might be that the number of subjects providing data to an analysis

is smaller than the number of subjects in the FAS. In addition, missing baseline values will not be imputed.

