#### **9.4.4 Supportive analyses**

Sensitivity analyses will be performed as follows:

- Subjects fulfilling at least one of the following criteria will be classified as non-responders with respect to PASI 75 and IGA 0 or 1 response at Week 68 and the Cox proportional hazards regression analysis of the primary analysis will be repeated:
  - subjects with missing injection (s) up to Week 68,
  - dropouts due to AEs, unsatisfactory therapeutic effect up to Week 68, and
  - subjects with missing data at Week 68.
- PASI 75 will be evaluated using Cox proportional hazards regression as described above with multiple imputations instead of non-responder imputation for missing values. Within this analysis the PASI score will be imputed and response variables will be derived based on the imputed scores. For each treatment group values will be imputed separately. Further details will be given in the analysis plan.

In addition, the secukinumab treatment groups will also be compared, i.e. a Cox proportional hazards regression will be fitted as described above including all four treatment groups. Placebo (secukinumab 150 mg in core studies) and Placebo (secukinumab 300 mg in core studies) will be compared as well as secukinumab 150 mg and secukinumab 300 mg.

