## 1.9.4 Handling of missing values/censoring/discontinuations

#### For the analyses re-run during RW period

The loss of PASI 75 response during RW period will be re-run. The subjects who have no lost PASI 75 response during RW will be considered as censored observations. Subjects who have not lost PASI 75 response but with missing values during RW will be considered as censored at prior available visit. Subjects who administered psoriasis concomitant medication (as per [MAP Appendix]), will be considered as failures at time of first administration if this occurred before the loss of PASI 75. Subjects who did not have PASI 75 response but randomized in RW period will be censored at day 0. Subjects with missing values at week X (X <156) and who have not lost PASI 75 response earlier, will be censored at week X (if they have not dropped out due to lack of efficacy or not administered psoriasis concomitant medication). Subjects who drop-out due to lack of efficacy will be considered as failure at time of drop-out. If drop-out was due to other reason, subjects will be considered as censored at time of drop-out. Intermediate missing values will not be considered.

Other time-to-event analyses will be handled analogously. For imputation techniques, please refer to Table 1-16.

For other analyses (not time to event) missing values with respect to response variables based on PASI score and IGA mod 2011 score will be imputed with multiple imputation regardless of the reason for missing data (e.g., premature study discontinuation, missed visit, administrative issues).

Following the intent-to-treat principle for subjects who prematurely discontinue treatment, but who are observed in the follow-up period, efficacy data collected in follow-up periods will be linked to planned but missed study visits as well, following imputation schemes described in Sections 1.5.4.1 and 1.9.4.2. (e.g., if a subject discontinues treatment at Week 56, but has follow-up visit F4, the PASI score observed at Visit F4 might be used for Week 60 assessments).

Novartis	Confidential	Page 39
RAP Module 3	9-Apr-2018 (1:15)	Secukinumab / AIN457A2302E1

For rebound and relapse no imputed data will be used and analyses will be based on observed data only.

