The last observation carried forward method (LOCF) will be applied to PASI score and IGA mod 2011 score that are missing after baseline regardless to the reason for missing data (e.g. premature study discontinuation, missed visit, administrative issues). Note that LOCF imputations will not be considered for response variables based on PASI score or IGA score which will be imputed with non-response, see above. Baseline values will not be carried forward.

If all post Randomization Visit efficacy values are missing for one efficacy parameter then these missing values will not be imputed and this subject will be removed from the analysis of the corresponding variable, *i.e.*, it might be that the number of subjects providing data to an analysis is smaller than the number of subjects in the FAS. In addition, missing baseline values will not be imputed.

For subjects who were re-treated after relapse with secukinumab 150 mg or secukinumab 300 mg amongst PASI 75 responders at week 52, values of RW period are not carried forward to treatment period.

For HAQ score and derived variables, EQ-5D and DLQI missing values will be replaced by LOCF. Missing responses will also be imputed by LOCF. Baseline values will not be carried forward.

The laboratory values below Lower Level Of Quantification (LLQ) or above Upper Level of Quantification (ULQ) will be imputed as LLQ or ULQ, respectively. The numerical part of the reported result will be treated as the actual LLQ or ULQ. These laboratory values will be displayed in listings using the standard unit with the reported sign ("<" or ">")."

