# 1.9.4.1 Details for imputations (non- responder and LOCF) and visit windowing

Note: These details are not applicable to time to event analysis. Only PASI and IGA mod 2011 based response variables are imputed with non-response, other response variables (e.g. for HAQ-DI, EQ-5D, DLQI) will be imputed with LOCF. Baseline values will not be carried forward. If all post baseline values are missing for one efficacy parameter, then these missing values will not be imputed and this subject will be removed from the analysis of the corresponding variable.

- Non- responder imputation for subjects with PASI 75 response at Week 52 RW period (Week 52 up to Week 156)
  - 1. Assign period to each visit as per CRF visit (CRF period) or as per visit date for unscheduled visits (analysis period)
  - 2. Assign analysis visit windows (for RW period from week 52 up to Week 156) according to Section 1.5.4. Of note, RW CRF period visits will not be assigned to treatment analysis period, whereas follow-up period CRF visits might be assigned to RW analysis period for subjects who do not enter treatment CRF period)
  - 3. If no CRF visit is assigned to an analysis visit as per Section 1.5.4, impute non-response

Note – Subjects with PASI 75 response at week 52 enter RW period. RW period is not fixed for all the subjects but varies for subject to subject based on occurrence of relapse. Subjects in RW period will enter treatment period only after first full relapse, if it occurs; otherwise not. Partial responders are not entering the RW period but go into the treatment period.

- LOCF imputation
- 1. Assign period to each visit as per CRF visit (CRF period) or as per visit date for unscheduled visits (analysis period)
- 2. Assign analysis visit windows (for RW period from week 52 up to Week 156) according to Section 1.5.4. Of note, RW CRF period visits will not be assigned to treatment analysis period, whereas follow-up CRF period visits might be assigned to RW analysis period for subjects who do not enter treatment CRF period)
- 3. If no CRF visit is assigned to an analysis visit as per Section 1.5.4, impute with LOCF

Note: All data collected in the eCRF will be considered for LOCF imputation regardless of whether the data was considered in analysis visit windows.

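### The SAP gives two conflicting rules for missing PASI/IGA response in the randomised withdrawal re-run, and its multiple imputation rule stops at Week 68 although the method is assigned to later visits

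*SAP*

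**What the plan says.** SAP 1.9.4, under the heading for analyses re-run during the RW period, states that outside time-to-event analyses missing PASI- and IGA-based response "will be imputed with multiple imputation regardless of the reason for missing data". Further down, under the same heading, LOCF is ruled out for "response variables based on PASI score or IGA score which will be imputed with non-response, see above".

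SAP 1.9.4.1 takes the second line: "Only PASI and IGA mod 2011 based response variables are imputed with non-response". It gives steps for the RW period up to Week 156, the last being "If no CRF visit is assigned to an analysis visit as per Section 1.5.4, impute non-response".

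SAP 1.9.4.2 describes multiple imputation (MI). It begins with loss of PASI 75 and then widens the scope: "Multiple imputation will also be used for PASI/IGA score and responses variables". It limits the data with "Values post assessment timepoint of the primary endpoint will not be considered for imputations". The example PROC MI variable list ends at Week 68. The text after it asks for the first visit with loss of PASI 75, but the example data step derives response only at the primary-endpoint week.

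Protocol 9.4.3 says missing PASI/IGA response "will be imputed with non-response regardless of the reason for missing data". Protocol 9.4.4 keeps MI as a supportive analysis of PASI 75, "with multiple imputations instead of non-responder imputation for missing values".

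SAP section 1 says the analysis follows protocol section 9, and the list of changes in SAP 1.1.1 does not mention MI. SAP 1.1 and 1.9.2 say the Week 68 primary analysis is not repeated and that loss of PASI 75 over the RW period is analysed instead. For the final analysis, SAP 1.9.4 uses observed cases, with MI as the sensitivity method for subjects on secukinumab from Week 52.

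**The concern.** A programmer following SAP 1.9.4 and one following 1.9.4.1 would produce different RW response tables from the same data. These tables carry the by-visit response rates and the Cochran-Mantel-Haenszel and logistic comparisons with placebo described in SAP 1.9.6.

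If MI is chosen, the only specification excludes everything after Week 68. Most of the visits to which MI is assigned come later, and the Week 68 analysis for which such a cut-off makes sense is not run under this SAP.

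Two smaller gaps sit in the same text. MI is assigned to IGA, but only change in PASI is modelled. PASI and IGA scores are given LOCF in 1.9.4 and MI in 1.9.4.2.

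If the choice is left open, it would be made after the data are known, for analyses that compare secukinumab with placebo.

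**Working it through.** **The plan's own figure.** The plan gives none on this point. Its one reproducible design figure is power above 90% (SAP 1.11). The hazard ratio is ln(0.90)/ln(0.77) = 0.403, and expected events are 276 × 0.10 + 138 × 0.23 = 59.3. The Schoenfeld formula at one-sided 2.5% gives 91.0%, so the figure reproduces. It concerns the Week 68 endpoint and does not depend on the rules discussed here.

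**The rules side by side (missing RW response, not time to event).**

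| Place | Rule |
|---|---|
| Protocol 9.4.3 | Non-response |
| Protocol 9.4.4 | MI, supportive, PASI 75 |
| SAP 1.9.4, first statement | MI |
| SAP 1.9.4, LOCF paragraph | Non-response, pointing back to text that says MI |
| SAP 1.9.4.1 | Non-response, Week 52 to Week 156 |
| SAP 1.9.4.2 | MI for scores and responses |

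Nothing ranks these. The pointer to Table 1-16 for imputation techniques does not help, because the list of tables shows that as a safety table.

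**Visits after the cut-off.** The primary variable runs to Week 68 (protocol 9.4.1). Scheduled visits come from SAP Table 1-5.
- Post-baseline RW visits, Weeks 56 to 156 every 4 weeks: (156 − 56)/4 + 1 = 26.
- Visits up to Week 68: 56, 60, 64 and 68, so 4. After it: 26 − 4 = 22.
- Open-label site visits: 168, 180, 192, 208, 220, 232, 244 and 260, so 8, all after the cut-off.

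Two limits apply. Comparisons with placebo stop at the last visit with more than 5% of subjects in the placebo group (SAP 1.9.6), so fewer than 22 may matter for the tests. The end of the final analysis at Week 260 is inferred from the on-treatment period in SAP 1.3.

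**Size of an extended model.** The example list has 9 distinct variables: 4 covariates, Week 52 and 4 visits. That is 9 + 9 × 10/2 = 54 means, variances and covariances. Carried to Week 156 it has 4 + 1 + 26 = 31 variables, hence 31 + 31 × 32/2 = 527, against 138 planned placebo subjects per dose. Lengthening the list alone may give a model that cannot be estimated.

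**How the two rules differ.** With observed response p and share missing m, non-response gives p(1 − m). MI gives about p if it returns the observed rate. The within-arm gap is p × m. The documents give neither p by visit nor m, so these values are assumptions:

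| p | m = 5% | m = 10% | m = 20% |
|---|---|---|---|
| 60% | 3 points | 6 points | 12 points |
| 80% | 4 points | 8 points | 16 points |

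The difference between arms changes by the difference of the two gaps. With 10% missing in both arms and 80% versus 60% response, that is 8 − 6 = 2 points. Unequal missingness could make it larger.

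**The case against.** **MI is visibly the sensitivity method.** SAP 1.9.4.2 introduces MI as a replacement for non-responder imputation. That sentence is about loss of PASI 75, however, and SAP 1.9.4 assigns MI to by-visit response outright.

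**Non-response is obviously the intended rule.** A reader might infer this from the protocol. The documents do not settle it. The SAP 1.9.4 sentence closely follows protocol 9.4.3 with MI put in place of non-response, which could equally be a deliberate edit that left 1.9.4.1 behind. These analyses were also run before (SAP 1.1), and the rule used then cannot be seen. This objection stands, so the remedy should not presume either rule.

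**The code is only an example.** SAP 1.9.4.2 says the procedure can be used in that way, so the visit list and data step are illustrative. The cut-off sentence is not; it is a stated rule, and it alone places 22 RW visits out of reach.

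**RW visits after relapse have no rule at all.** A reader might infer this from the last step of SAP 1.9.4.1, which read literally turns every empty visit into non-response. The rest of the SAP points the other way. RW ends at relapse (1.3), treatment-period assessments do not count for RW (1.5.4), the note in 1.9.4.1 says RW length varies, and the 5% limit in 1.9.6 presupposes that the placebo group shrinks. Only a clarifying clause is needed.

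**The effect can be sized from the planning values.** The 10% and 23% in SAP 1.11 are cumulative loss up to Week 68. They are not by-visit response, since a subject can lose and regain PASI 75, and Week 68 lies inside the imputation list.

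**Conclusion.** The point holds on the text. For the same RW response variables the SAP prescribes MI and non-response without a hierarchy, and no departure from the protocol is recorded. The MI rule shuts out values after Week 68, while MI is assigned to RW response up to Week 156 and to the final-analysis sensitivity method. The missing IGA model and the LOCF/MI conflict for scores are equally plain.

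Its reach is limited. The affected analyses are secondary or sensitivity analyses outside the testing strategy (SAP 1.9.3). A reader might infer that the Week 68 primary result or the main final results are in doubt. The documents do not support that: the primary analysis is not run under this SAP, and the final response results are observed case. Time-to-event analyses also have their own censoring rules (SAP 1.9.4 and 1.9.7).

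The size of the effect on results cannot be derived. No missing-data rate for the extension is given, and linking follow-up assessments to missed RW visits will reduce missingness. The gaps in the working rest on assumed response and missingness. The visit counts rest on Table 1-5 and on reading the primary-endpoint timepoint as Week 68. That the cut-off was carried over from the Week 68 analysis is likely, but an inference.

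**What to change.** (a) In SAP 1.9.4, name one main rule and one sensitivity rule for missing RW response, consistent with the previous run of these analyses. Delete the conflicting text, either in the first statement of 1.9.4 and in 1.9.4.2, or in the LOCF paragraph and in 1.9.4.1. If the main rule departs from protocol 9.4.3, list that in SAP 1.1.1.

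(b) In SAP 1.9.4.2, delete the cut-off sentence and extend the visit list to the visits actually analysed. Change the example data step so that response is derived at each visit and first loss is found across visits. Specify a simpler fallback model in case the extended one cannot be estimated in the placebo arms.

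(c) Add an imputation model for IGA or drop MI for IGA. State whether LOCF or MI applies to PASI and IGA scores.

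(d) Add a clause to the last non-response step in SAP 1.9.4.1 that RW visits after relapse are not imputed, in line with 1.3, 1.5.4 and 1.9.6.

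The cost is SAP wording and programming. No data collection, sample size or alpha changes.
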